6.8.7 Summary of Study-specific Procedures

Table 5. Schedule of study-specific procedures

Elapsed Time After Dose (hh:mm)	Pupillometry, Dark-Adapted	Vital Signs RR, CO ₂ , HR	Vital Signs BP, SpO ₂	Observed Sedation, MOAA/S	Thermal Pain Threshold	Subjective Self Assessment, VAS
Baseline draw	X	X	X	X	X	X
Start IV dose						
0:02 ± 0:01	X	X			X	
0:04 ± 0:01	X	X		X		X
0:06 ± 0:01	X	X			X	
0:08 ± 0:01	X	X				
0:10 ± 0:01	X	X	X	X	X	X
0:12 ± 0:01	X	X				
0:15 ± 0:01	X	X				
0:20 ± 0:01	X	X				
0:30 ± 0:02	X	X				
0:40 ± 0:02	X	X		X	X	X
0:50 ± 0:02	X	X				
1:00 ± 0:05	X	X	X	X	X	X
1:30 ± 0:05		X		X		X
2:00 ± 0:10	X	X	X	X	X	X
3:00 ± 0:10		X		X		X
4:00 ± 0:10	X	X	X	X	X	X
6:00 ± 0:30		X	X	X		X
8:00 ± 0:30	X	X		X	X	X
10:00 ± 0:30		X		X		X
12:00 ± 0:30	X	X	X	X	X	X
18:00 ± 0:30						
24:00 ± 1:00	X	X		X	X	X
30:00 ± 1:00	X	X	X	X	X	X
48:00 ± 8:00	X	X	X	X	X	X
72:00 ± 8:00	X	X	X	X	X	X
96:00 ± 8:00	X	X	X	X	X	X

Some timepoints have multiple tasks scheduled. It is suggested that the tasks be prioritized in order of: obtaining the PK sample, pupillometry, vital signs, observed sedation, thermal pain threshold, and subjective self-assessment. These tasks are not all performed during all the timepoints, please follow Tables 4 and 5 above. The research staff does have the discretion to perform the task order according to their trained judgement as long as they are within the timepoint parameters.

6.9 Study-specific PK Specimen Preparation, Handling, Storage, and Shipping

Biological samples collected for the purposes of this research will be labeled only with a unique accession number (via study-provided barcode label) without protected health information (PHI) that can directly identify the study participant. These samples will be sent to the PTN-designated laboratory for analysis (i.e., methadone concentration measurements). Once samples are analyzed, data will be entered into the study records. After all study-related testing is complete, any remaining samples will be shipped to an NIH-designated biorepository for future unspecified use, unless prohibited by local ethics committee or regulatory agencies (see Section 12).

Refer to the MOP for instructions for the collection, labeling, preparation, handling, and storage of specimens.

7 STUDY PRODUCT DESCRIPTION

7.1 Study Product Information

Methadone hydrochloride is a mu-agonist; a synthetic opioid with multiple actions qualitatively similar to those of morphine. The most prominent action involves the central nervous system and organs composed of smooth muscle. Methadone's principal therapeutic uses are for analgesia and for detoxification or maintenance in opioid addiction. Specific PK and PD qualities of methadone are in the FDA drug label.²⁹

7.1.1 Dosage and Dose Timing

Each participant will be administered a single dose of IV methadone at 0.1 mg/kg per measured body weight. The single dose will be calculated to the closest 0.1 mg.

7.1.2 Formulation, Packaging, and Labeling

Methadone Hydrochloride Injection USP, 10 mg/mL from Mylan Institutional LLC will be used for this study.³³ It is supplied as 20-mL multi-dose vials. Each mL of Methadone Hydrochloride Injection USP contains 10 mg (0.029 mmol) of methadone hydrochloride. The injectable solution contains the following inactive ingredients: chlorobutanol, 0.5%, as a preservative, and sodium chloride.

Refer to MOP for details.

7.1.3 Product Storage and Stability

Methadone Hydrochloride Injection USP should be stored at 20 to 25°C (68 to 77°F), with excursions permitted between 15 to 30°C (59 to 86°F). It should be protected from light and stored in carton until contents have been used.

Refer to MOP for details.

7.1.4 Preparation and Administration

Methadone will be prepared by Duke Investigation Drug Services (IDS). Each participant will receive 0.1 mg of methadone per kg of body weight from the 10 mg/mL stock concentration administered via IV push. Methadone (0.1mg/kg bw) will be administered via IV push followed by 3mL flush over 2 minutes. The time IV push begins and the time flush ends will be documented on the source.

Refer to MOP for details.

7.2 Accountability Procedures for the Study Product

Methadone hydrochloride will be prepared by Duke Investigational Drug Services and administered intravenously to participants by study nurses.

Refer to MOP for details.

7.2.1 Replacement Doses

If the product dose is broken or unusable, study personnel will prepare study product from a new vial. Replacement doses may be requested by contacting the Duke Investigational Drug Services.

See MOP for contact information.

7.2.2 Disposition of Study Products Upon Study Completion or Expiration

Upon completion of the study, or upon notice of the study products' expiration, the study products should be disposed of at the site, pursuant to the ICH/GCP guidelines and the Duke Investigational Drug Services policy for drug destruction.

See MOP for details.

7.3 Concomitant Medications/Treatment Restrictions

Participants should not receive serotonergic drugs within 7 days prior to drug administration or during treatment or follow-up period (up to 96 hours). Participants should not receive inhibitors or inducers of CYP2B6 within 30 days prior to enrollment or during the study period. See Section **5.2** for a listing.

Participants will be required to abstain from the following:

- *30 days before study-drug administration:* non-study medications (including over the counter and/or herbal), without prior PI approval – non-study medications that are given per standard of care and are not exclusionary will receive approval, at the discretion of the Study PI.
- *24 hours before study-drug administration and during study days:* alcohol
- *8 hours before study-drug administration:* food
- *4 hours before study-drug administration:* liquids
- *Day of administration:* alcohol and caffeine

Current substance or drug dependence will be confirmed by positive urine drug screen at the screening/enrollment visit. Current alcohol abuse will be confirmed by positive breathalyzer at the screening/enrollment visit.

Ondansetron (4 mg IV) will be administered 15 minutes prior to methadone administration to decrease or prevent nausea. If initial dose is not efficacious, and nausea persists, intravenous metoclopramide (10 mg) will be provided.

The date, time, route, and dose of all concomitant medications of interest will be recorded.

8 ASSESSMENT OF SAFETY

8.1 Specification of Safety Parameters

Studies performed under IND FDA regulations require reporting based on the definition included in 21 CFR 312.32 (a), regardless of the definition of AE used in the protocol.

An **adverse event (AE)** is any untoward medical occurrence in humans, whether or not considered intervention-related, which occurs during the conduct of a clinical trial. (Any change in clinical status, ECGs, routine labs, x-rays, physical examinations, etc., that is considered clinically significant by the Study PI is considered an AE).

An **unexpected adverse event** is any AE, of which the nature, specificity, or severity is not consistent with the applicable product information (e.g., package insert/approved label) or investigational plan.

A **suspected adverse reaction (SAR)** is any AE for which there is a reasonable possibility that the intervention caused the AE. A reasonable possibility implies that there is evidence that the intervention caused the event.

An **adverse reaction (AR)** is any AE caused by the intervention.

A **serious, unexpected, suspected adverse reaction (SUSAR)** is a SAR that is both serious and unexpected.

All AEs related to methadone administration will be reported. Safety will be assessed by frequency and incidence of reported AEs, SAEs, and SUSARs. A safety Data Monitoring Safety Monitoring Board (DSMB) convened by NICHD will review data and safety information from study participants.

All AEs related to the study procedures or assessments (e.g., blood draws) and SUSARs related to study product will be reported. Safety ESIs will be recorded.

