8.5 Collection Period and Reporting Procedures

Adverse Event information will be gained from direct monitoring of the study participants as well as from clinician observation and self-reporting by the study participants. The investigator/delegate (defined as a clinician licensed to make a diagnosis) must document his or her assessment of severity and causality in the participant records in a timely manner and submit safety reports as required by his or her IRB.

Death irrespective of causality, identified as either an unsolicited or solicited event (i.e., SESI), at any time through end of study will be reported.

Serious Adverse Events/SUSARs will be collected for all participants, following the execution of informed consent through 7 days post last sample collection, and reported on the AE/SAE electronic case report form (eCRF).

Safety ESIs (Section **4.6.1** and **8.4.1**) will be collected for all participants following the execution of informed consent through 7 days post last sample collection, and assessed for intensity, causality, and association, and reported in the data system. To determine if SESIs are dose related, additional data around solicited safety events will be recorded.

Adverse Events will be recorded from the time of methadone administration until 96 hours (the final study visit) and reported in the data system.

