8.6 Safety Event Follow-up and Sponsor Reporting

Adverse Events, SAEs, and SESIs **directly related** to study intervention/procedures will be followed until resolution, even if this period extends beyond the study-reporting period.

Resolution of an AE is defined as the return to pretreatment status or stabilization of the condition with the expectation that resolution will remain chronic. If the event resolves during the study or follow-up period, a resolution date should be documented in the data system.

Adverse Events **directly related** to study intervention/procedures and SESIs (without a causal relationship to study intervention, that are not defined as an SAE) will be reported in the data system within 7 days of identification/site awareness.

Adverse Events considered related to study intervention/procedures and all SAEs/SESIs ongoing at the time of the last dose of study intervention will be followed for as long as necessary to adequately evaluate the participant's safety or until the event stabilizes. If the event resolves during the study or follow-up period, a resolution date should be documented in the data system.

Serious Adverse Events, SUSARs, and SESIs that are associated with any of the criteria that define the event as an SAE will be reported in the data system within 24 hours of identification/site awareness. Upon entry in the Electronic Data Capture (EDC) system, these events will generate an automatic email notification to the MM and the sponsor. The investigator/delegate (defined as a clinician licensed to make a diagnosis) must document his or her assessment of intensity, causality, and association in the participant records in a timely manner and submit safety reports as required by his or her IRB.

The MM will review all safety events at the time they are reported. Any event that requires expedited reporting based on federal regulations (21 CFR 312.32) will be forwarded to the IND sponsor. The IND sponsor or its representative will submit expedited safety reports (e.g., IND safety reports) to the regulatory agencies, as necessary.

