11.1.2 Secondary Endpoints

The list of secondary endpoints includes the following:

- Change in pupillometry
- Observed sedation
- Thermal pain tolerance thresholds
- VAS from pre-dose to post-dose
- Proportion of participants reporting AE, SAE, SUSAR from baseline to the end of safety follow-up
- QTc from baseline to the end of safety follow-up

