11.3.2 Secondary Analysis

1) The relationship between methadone concentrations/other PK parameters and endpoints of change in pupillometry, observed sedation levels, thermal pain tolerance thresholds, change in VAS from pre to post dose, and change in respiratory rate will be evaluated using standard descriptive statistics. Descriptive summaries of the endpoints predose, postdose, end of follow-up will be presented. The change between time points also will be presented, along with the 95% CI, t-test, and p-value.

2) The following endpoints will be analyzed in the safety analyses:

Incidence of safety related events

- A. AE related to study procedure
- B. SAE related to study procedure
- C. SUSAR related to study drug
- D. Safety Events of Special Interest (QTc prolongation)

In addition, changes in QTc interval will be assessed over time.

All AEs recorded during the study period will be coded with Medical Dictionary for Regulatory Activities (MedDRA) Version March 2018. Summaries of AE will be tabulated for the following types:

- A. Number (%) of participants with any AE
- B. Number (%) of participants with any SAE
- C. Number (%) of participants withdrawn from treatment due to SUSAR

All summaries will be reported in total and by study site.

Additional analyses (e.g., Exposure-Response [safety] analysis) and summaries may be derived if deemed appropriate and will be further described in the SAP.

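### Section 8.1 names only related AEs as those to be reported, the tolerability endpoint counts any AE, no section says which rule prevails, and the 11.3.2 incidence list omits methadone-related non-serious AEs

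*Combined protocol and SAP*

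**What the plan says.** **Definition.** Section 8.1 says an adverse event "is any untoward medical occurrence in humans, whether or not considered intervention-related, which occurs during the conduct of a clinical trial".

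**Reporting, Section 8.1.** Two sentences later in the same section are limited by causality. For the drug: "All AEs related to methadone administration will be reported. Safety will be assessed by frequency and incidence of reported AEs, SAEs, and SUSARs". For procedures: "All AEs related to the study procedures or assessments (e.g., blood draws) and SUSARs related to study product will be reported".

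**Collection, Section 8.5.** No relatedness condition appears: "Adverse Events will be recorded from the time of methadone administration until 96 hours (the final study visit) and reported in the data system". SAEs and SUSARs are collected from consent to 7 days after the last sample, also without a causality condition.

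**Deadlines, Section 8.6.** The 7-day entry rule applies to AEs directly related "to study intervention/procedures and SESIs (without a causal relationship to study intervention, that are not defined as an SAE". SAEs, SUSARs and serious SESIs have a 24-hour rule. Non-serious AEs judged unrelated have no deadline.

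**Endpoint and analysis.** Section 11.1.2 gives the endpoint as "Proportion of participants reporting AE, SAE, SUSAR from baseline to the end of safety follow-up", and Section 3 agrees. Section 11.3.2 codes all recorded AEs and tabulates "Number (%) of participants with any AE". Before that, the same section lists the endpoints of the safety analysis as procedure-related AEs, procedure-related SAEs, drug-related SUSARs and QTc prolongation.

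**The concern.** The tolerability numerator can be read in two ways. In one, it is every participant with an AE. In the other, it is every participant with an AE that the investigator attributed to methadone or to a procedure. Section 8.1 points to the second reading, because it rests the safety assessment on reported AEs and names only related ones as reported. The endpoint definitions point to the first.

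Tolerability is a secondary objective, and the study is open-label with a single arm. If causality decides what is entered, a row labelled as any AE would hold only AEs judged related, and a reader of the table could not tell. The error runs one way, because removing events can only lower the proportion.

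The 11.3.2 list raises a separate difficulty. Methadone-related non-serious AEs are the events most relevant to the objective, yet they are not named among the safety endpoints and have no row of their own in the tabulation.

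**Working it through.** **1. The rules side by side, for a non-serious AE judged unrelated to drug and procedure**

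| Place | What it governs | Is the event covered? |
|---|---|---|
| 8.1, definition | what an AE is | yes |
| 8.1, reporting sentences | what is reported, and the basis of the safety assessment | not named |
| 8.5 | what is recorded and put in the data system | yes |
| 8.6 | follow-up and entry deadlines | no deadline given |
| 3 and 11.1.2 | endpoint | yes |
| 11.3.2, list of safety endpoints | incidence analysis | no |
| 11.3.2, tabulation | any-AE row | yes |

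No section ranks these rules.

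**2. Such an event is plausible.** Section 7.3 gives every participant IV ondansetron before methadone, and Section 2.4 says that ondansetron can cause headache. A headache attributed to ondansetron is arguably neither methadone-related nor procedure-related. The 8.1 reporting sentences do not name it, but 8.5 requires that it be recorded.

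**3. The 11.3.2 list against the objective.** A non-serious AE judged related to methadone fits none of the four listed endpoints unless it is QTc prolongation. It enters the any-AE row, but no row isolates it.

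**4. Size.** The plan states no AE rate or precision target for tolerability, so there is no figure to reproduce. With about 20 participants (Section 5.1), one participant counted differently moves the proportion by 1/20 = 5 percentage points.

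The number affected can only be illustrated with assumed rates. Let pR be the probability that a participant has a related AE. Let pU be the probability of an unrelated AE among participants without a related one.

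- Expected participants counted differently = n(1 − pR)pU
- Probability that at least one differs = 1 − [1 − (1 − pR)pU]^n

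Results at n = 20:

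| pR | pU | Expected participants | Points | P(at least one) |
|---|---|---|---|---|
| 0.3 | 0.20 | 20 × 0.7 × 0.20 = 2.8 | 14 | 0.95 |
| 0.5 | 0.05 | 20 × 0.5 × 0.05 = 0.5 | 2.5 | 0.40 |
| 0.5 | 0.10 | 20 × 0.5 × 0.10 = 1.0 | 5 | 0.64 |
| 0.5 | 0.20 | 20 × 0.5 × 0.20 = 2.0 | 10 | 0.88 |
| 0.9 | 0.05 | 20 × 0.1 × 0.05 = 0.1 | 0.5 | 0.10 |
| 0.9 | 0.20 | 20 × 0.1 × 0.20 = 0.4 | 2 | 0.33 |

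Over pR from 0.3 to 0.9 and pU from 0.05 to 0.20, the expected gap runs from 0.1 to 2.8 participants. For scale, the exact (Clopper-Pearson) 95% interval is 27% to 73% for 10/20 and 36% to 81% for 12/20.

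**The case against.** The best defence is that 8.5 is the section on collection, is explicit and has no filter. Section 11.3.2 codes the AEs that were recorded, which is the verb 8.5 uses. Section 8.6.1 puts AEs of withdrawn participants in the EDC without a causality condition, and Section 16.3 enters AEs as clinical data without one. On that reading the any-AE count is right and 8.1 is loosely worded. This stands as far as it goes: if 8.5 is followed, the numerator is sound. It does not remove the conflict, because 8.1 is the sentence that ties the safety assessment to reported AEs.

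The effect may also be slight. After an IV opioid, repeated blood draws and heat stimuli, a participant with any AE probably has a related one and is counted under both rules. This stands too. When 90% have a related AE, the expected gap is at most 0.4 of 20 participants over the pU range shown.

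A reader might infer more than the documents support:

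- *Unrelated AEs are barred from the database.* Neither 8.1 nor 8.6 says so; the restriction is implied.
- *Section 8.6 defines the numerator.* It sets follow-up and deadlines. A missing deadline bears on when an event is entered, and 8.5 still requires entry.
- *Directly related is a stricter standard than the one in 8.4.* The term is undefined, and 8.6 also speaks of events considered related. It cannot be ranked.
- *Omitted events are lost.* Sections 8.4 and 16.2 require causality assessment, 8.4 requires it to be documented in participant records, and Section 13 gives access to source. An event could be in source and absent from the EDC.
- *Sites will differ.* There is one site.

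**Conclusion.** The plan is wrong as written, in two places. Section 8.1 names only related AEs as reported, against the unfiltered rule in 8.5 and the endpoint in Sections 3 and 11.1.2. Within 11.3.2, the list of safety endpoints does not match the tabulation and leaves out methadone-related non-serious AEs.

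The exposure is confined to non-serious AEs judged unrelated. It is a risk that depends on which rule the site follows. If it materialises, it understates the AE proportion by 5 points per affected participant at n = 20. The total cannot be stated, because the documents give no AE rate; the gaps computed above rest on assumed rates and include very small values. The endpoint is descriptive, with no comparator, so no between-group comparison or test of the AE proportion is affected. The case for acting is that the filter works in one direction, would not show in the table, and costs almost nothing to remove.

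**What to change.** - **Section 8.1:** replace the two causality-limited reporting sentences. State that all AEs in the 8.5 collection window are recorded in the eCRF regardless of causality, with the 8.4 causality assessment entered as a field.
- **Section 8.6:** replace the undefined term *directly related* with the 8.4 category. Keep relatedness as a criterion for follow-up only. An entry deadline for unrelated non-serious AEs would be optional tidying.
- **Section 11.3.2:** replace the AE, SAE and SUSAR items of the list with rows for any AE, AEs suspected to be related to methadone, and AEs related to procedures, and the same three rows for SAEs.

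The cost is protocol wording and a few more AE lines to enter. No visit or assessment is added. The reported AE rate may come out slightly higher.

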8.2 Guidelines for Assessing Association of an Adverse Event

A **serious adverse event (SAE)** or **serious suspected adverse reaction** or **serious adverse reactions** determined by the investigator or the sponsor is an AE or SAR that results in any of the following outcomes:

- Death
- Life-threatening AE (“life-threatening” means that the study participant was, in the opinion of the investigator or sponsor, at immediate risk of death from the reaction as it occurred and required immediate intervention)
- Persistent or significant incapacity or substantial disruption of the ability to conduct normal life functions
- Inpatient hospitalization or prolongation of existing hospitalization
- Congenital abnormality or birth defect
- Important medical event that may not result in one of the above outcomes, but may jeopardize the health of the study participant or require medical or surgical intervention to prevent one of the outcomes listed in the above definition of serious event.

8.3 Guidelines for Assessing Intensity of an Adverse Event

Safety events will be assessed by the study clinician using a protocol defined grading system.

The investigator/delegate (defined as a clinician licensed to make a diagnosis) should use the following definitions when assessing intensity of an adverse event:

- **Mild** - Participant is aware of symptoms or has minor findings but tolerates them well, and no or minimal intervention required
- **Moderate** - Participant experiences enough symptoms or findings to require intervention
- **Severe** - Participant experiences symptoms or findings that require significant intervention

8.4 Guidelines for Assessing Causality

The investigator/delegate (defined as a clinician licensed to make a diagnosis) will use the following question when assessing causality of an AE to study intervention: Is there a reasonable possibility that the intervention caused the event? “Reasonable possibility” means that there is evidence to suggest a causal relationship between the study intervention and the AE. An affirmative answer designates the event as a suspected adverse reaction.

The investigator/delegate (defined as a clinician licensed to make a diagnosis) must document his or her assessment of intensity, causality, and association in the participant records in a timely manner and submit safety reports as required by his or her IRB.

